3.7.4. Sample Retention

Placental biopsies and unused blood and breastmilk/chestmilk samples will be stored at the SCC for future research (e.g., placenta immunohistochemistry, metabolomic analyses). Banked samples, when paired with the detailed PLAN-V dataset will be an important resource for future research.

Objective 3 - COPE Sub-study

Comparing immune responses to COVID-19 vaccination and natural COVID-19 disease among pregnant women/individuals and their infants exposed in utero

Study design: A cross sectional analysis of maternal and infant samples at the time of delivery.

Study Population: We will use samples collected at the time of delivery from mother-infant dyads who were enrolled in the current PLAN-V study and the PI's CIHR-funded COPE Network study (CTO ID 2168).³

[figure not shown]
- **PLAN-V study participants:** Mother-infant dyads in which mothers received at least one dose of the COVID-19 vaccine in pregnancy (any type). Eligible dyads will be those where mothers had no COVID-19 infection history and from whom maternal blood and infant cord blood samples were collected at delivery (i.e., vaccinated mother-infant dyads from the pregnancy group).
- **COPE Network study participants:** The COPE Network Study is an ongoing pregnancy and birth cohort study of mothers with documented COVID-19 infection during pregnancy.³ COPE Network study participants contributed both maternal blood and infant cord blood samples at delivery. Samples from more than 100 dyads have been collected to date.

Exposures: The exposure of interest is maternal COVID-19 vaccination (PLAN-V Study) or infection (COPE Network Study) in pregnancy.

Outcome Measures: **The primary outcomes are:** seroconversion rates and antibody titres in pregnant women/individuals after COVID-19 vaccination and COVID-19 disease in pregnancy; trans-placental transfer of antibodies to neonates with *in utero* exposure to COVID-19 vaccination compared to COVID-19 disease; and differences in antibody transfer to breast/chest milk where samples are available. (Breastmilk/chestmilk samples are available from 50% of COPE Network participants). **Secondary outcomes** will be the nature and frequency of pregnancy and newborn outcomes at delivery.

Sample analysis. Maternal and newborn cord blood serum samples collected at the time of delivery will be evaluated for SARS CoV-2 specific IgG and neutralizing antibody titres and IgG subclass distribution. Samples will be analyzed using the methods described in Section 3.7.3.

Data Sources: Immunogenicity data (including seroconversion rates and antibody titres), and data on participant characteristics (including sociodemographic information and pregnancy, delivery and newborn outcomes), will be obtained from the PLAN-V and COPE Network study datasets. The PLAN-V dataset has been purposefully aligned with that of the COPE Network Study thereby facilitating robust comparison of antibody and health outcome data. The COPE Network Study dataset includes comprehensive information on SARS-CoV-2 infection (date and gestational age of diagnosis, virus titres, symptomology, maternal and newborn case management) derived from the Ontario provincial birth registry, BORN Ontario, which has province-wide data collection on COVID-19 infection in pregnancy. The PLAN-V study data will be transferred to BORN for analysis.

Objective 4: SSO Sub-study

Comparing immune responses to COVID-19 vaccination between pregnant and non-pregnant women/individuals

Study design: A retrospective analysis of immunological data generated from two research studies

Study Population: We will use samples collected from mothers who were enrolled in the current PLAN-V study and the *Stop the Spread Ottawa (SSO)* study (OHSN: 20200481-01H; uOttawa: H-09-20-6135).³

[figure not shown]
- **PLAN-V study participants:** Women/Individuals who received at least one COVID-19 vaccine dose in pregnancy (any type). We will limit this analysis to women/individuals without known history of SARS-CoV-2 infection, and for whom maternal blood samples were collected.
- **Stop the Spread Ottawa (SSO) participants:** Non-pregnant females of reproductive age without known history of SARS-CoV-2 infection who received at least one COVID-19 vaccine dose. SSO is an ongoing Ottawa-based, 1000-person prospective cohort study designed to investigate the SARS-CoV-2-specific immune response on COVID-19 convalescent and COVID-19 vaccinated individuals. A total of 126 non-pregnant individuals of reproductive age who have received a COVID-19 vaccine have been enrolled to date. Participants provide monthly blood samples post-vaccination using the same protocols described for the PLAN-V study protocol and are followed for 10 months, allowing for comparison across the PLAN-V time points.

Exposures: The exposure of interest is maternal COVID-19 vaccination in pregnancy (PLAN-V Study) or while not pregnant (SSO Study)

Outcome Measures: The primary immunological outcome measure will be antibody titres acquired from COVID-19 vaccination in pregnant women/individuals will be compared to those of non-pregnant women/individuals. Secondary outcomes will include vaccine reactogenicity, as well as nature and frequency of vaccine-related adverse events.

Sample analysis. Blood serum samples will be evaluated for SARS CoV-2 specific antibodies and neutralizing antibody titres, as well as antibody subclass distributions where appropriate. Samples will be analyzed using the methods described in Section 3.7.3.

Data Sources: Immunogenicity data (including seroconversion rates and antibody titres), vaccine-related data (including product information, reactogenicity and adverse events), and participant characteristics (including sociodemographics, health behaviour risks and medical history) will come from the PLAN-V and the SSO study datasets. The PLAN-V and SSO datasets are both stored at the OHRI, and data elements are aligned thereby facilitating robust comparison of outcome measures.

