3.5.7. Premature Withdrawal/Discontinuation

[figure not shown]
Reasons for participant withdrawal from the study will be documented. If a participant no longer wants their samples to be used in this research, they can request to have their samples destroyed. However, samples will not be destroyed if they have been used in their entirety, or if they have been shared with a 3rd party. Collected data and test results from samples already collected for the study will be retained such that withdrawal will only affect future data or sample collection. Participants who withdraw from the study will no longer be contacted.

If a participant does not complete a study questionnaire, or does not contribute one or more study samples (by choice, or due to other factors) they are free to do so. Incomplete data or bio-sample collection will not exclude participants from the study.

An individual's participation may also be terminated prematurely at the request of the Site Investigator/Delegate, or the Study Coordinating Centre.

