3.6.2. Secondary Data collection

Obstetrical, delivery and neonatal outcome data will be extracted from patient medical charts and will include information on pregnancy complications (e.g., hypertensive disorders of pregnancy, diabetes in pregnancy), delivery (e.g., type and mode of delivery, type of labour, live/stillbirth outcome) and newborn outcomes (e.g., gestational age at birth, birthweight, Apgar scores, NICU admission, need for resuscitation, IV antibiotics and other medications, feeding method from birth to hospital discharge).

Chart reviews will also be conducted if additional information is required to complete/verify the maternal and infant(s) data collection, and/or new information is revealed through participant correspondence. Participants who have an unanticipated delivery at a non-participating hospital site or hospital site without research coordinator support will be asked to sign an 'authorization for release of information' form to allow the research team access to their medical records for data extraction.

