3.7. Sample Collection, Shipping and Analysis

3.7.1. Sample collection

Participants will be asked to contribute biological samples. We will allow participants to choose the scope of sample collection at each time-point. Samples will include maternal blood; breastmilk/chestmilk (postpartum collection only); and newborn blood (including cord blood at delivery). (Table 2)

Sampling will be coordinated alongside routine clinical collections where possible to minimize burden to participants. If participating hospital sites have sufficient capacity and resources, participants will be given the option to (1) return to the hospital or affiliated community clinic for sample collection/drop-off; (2) schedule a home visit with a research nurse/coordinator for sample collection/pick-up; (3) mail-in samples, if dried blood spot is preferred by the participant.

For the protection of all parties, both the Site Investigator/Delegate conducting the appointment and the participant will be directed to answer a series of self-assessment questions to assess likelihood or risk of COVID-19 infection before attending in-person visits.

[figure not shown]

Table 2. Sample collection schedule for vaccinated participants

	Visit 1	Post-vaccination Follow-up ³				Delivery
		Visit 2	Visit 3	Visit 4	Visit 5	
Maternal blood ¹	X	X	X	X	X	X
Baby(ies) blood ^{1,2}		X	X	X	X	
Breast/Chest milk ²		X	X	X	X	X
Cord blood						X
Placenta						X

¹Blood samples will be taken as peripheral blood draws, or as dried blood spot samples, as per participant preferences.

²Baby(ies) and milk samples will only be collected after delivery.

³Post-vaccination follow-up schedule will be the same for all vaccine doses (dose 1 or dose 2, if applicable).

- Visit 2 will be scheduled for ≥ 14 days after 1st dose and prior to 2nd dose
- Visit 3 will be scheduled for ≥ 14 days after 2nd dose and prior to visit 4
- Visit 4 will be scheduled for 90 days \pm 14 days after last dose
- Visit 5 will be scheduled for 180 days \pm 14 days after last dose
- If participant is getting a 2-dose vaccine, 1-month follow-up for data collection for dose 1 will occur before dose 2 administration.
- If participant is getting a 2-dose vaccine, and dose 2 scheduling is delayed (for any reason – federal/provincial/local recommendations, participant reasons), data and sample collection will be done approximately every 3 months (~120 days) until dose 2 is administered

Blood samples

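### Objective 3 reports chart-based pregnancy and newborn outcomes only in dyads with delivery blood samples, so the frequencies are conditional on sample collection and may be biased.

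*Protocol*

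**What the plan says.** The Objective 3 COPE sub-study (printed after Protocol section 3.7.4) defines one population. On the PLAN-V side, eligible dyads are those whose mothers were vaccinated in pregnancy, had no history of COVID-19 infection, and "from whom maternal blood and infant cord blood samples were collected at delivery". On the comparator side, "COPE Network study participants contributed both maternal blood and infant cord blood samples at delivery".

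The primary outcomes are serological. The secondary outcomes "will be the nature and frequency of pregnancy and newborn outcomes at delivery". No other population is named for them. The Data Sources paragraph of the sub-study takes pregnancy, delivery and newborn outcomes from the PLAN-V and COPE datasets and presents the alignment of those datasets as allowing both antibody and health outcomes to be compared.

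Four other places bear on the point:

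- Section 3.6.2: "Obstetrical, delivery and neonatal outcome data will be extracted from patient medical charts". For "Participants who have an unanticipated delivery at a non-participating hospital site or hospital site without research coordinator support", it describes a signed release of medical records and says nothing about samples.
- Section 3.7.1: "We will allow participants to choose the scope of sample collection at each time-point". Under Blood samples, it places cord blood collection straight after the birth.
- Section 3.5.7: "Incomplete data or bio-sample collection will not exclude participants from the study".
- Section 3.4.2 lists the main study's clinical outcomes, including fetal loss and stillbirth, with no sample requirement.

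**The concern.** The antibody and placental-transfer endpoints cannot be evaluated without paired blood, so the sample requirement is right for them. The clinical outcomes can be known without any sample, yet they inherit the same restriction.

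The restriction is not neutral. Cord blood is obtained, or not, at the delivery, after the exposure and at the moment when many of these outcomes occur. How and where the birth takes place can affect whether the sample is taken. A frequency calculated only among successful collections is then conditional on something that the outcome may influence.

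Two results are at stake: the outcome frequency in each cohort, and the comparison of vaccinated with infected mothers. Applying the restriction in both cohorts protects the comparison only if relative collection success, complicated against uncomplicated, is the same in each. The Protocol gives no basis for assuming that.

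**Working it through.** **What the text fixes.** Three statements side by side give the structure.

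1. Objective 3 eligibility requires both delivery samples.
2. The Objective 3 secondary outcomes are clinical and have no population of their own.
3. Section 3.6.2 and the Objective 3 Data Sources paragraph obtain clinical outcomes from charts and datasets.

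The sample requirement therefore removes dyads whose clinical outcomes may well be known. An unplanned off-site birth shows this most directly: section 3.6.2 provides for obtaining the record and makes no provision for cord blood.

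**Size.** The Protocol states neither collection rates nor expected outcome frequencies, so there is no figure of its own to reproduce. Section 1.2 counts more than 150 infected COPE participants, and Objective 3 counts samples from more than 100 dyads. These do not yield a collection rate, because the 150 includes women still awaiting delivery.

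Let p be the true frequency of an adverse outcome, c1 the proportion of affected deliveries with samples, and c0 the proportion of unaffected deliveries with samples.

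Observed frequency = p·c1 / [p·c1 + (1 − p)·c0]

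Equivalently, observed odds = true odds × (c1/c0), so the bias depends wholly on c1/c0. All values of p, c1 and c0 below are assumptions, with c0 = 0.80.

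| c1 | true 10% reads | true 5% reads |
|---|---|---|
| 0.30 | 0.030/0.750 = 4.0% | 0.015/0.775 = 1.9% |
| 0.40 | 0.040/0.760 = 5.3% | 0.020/0.780 = 2.6% |
| 0.60 | 0.060/0.780 = 7.7% | 0.030/0.790 = 3.8% |
| 0.80 | 0.080/0.800 = 10.0% | 0.040/0.800 = 5.0% |
| 0.90 | 0.090/0.810 = 11.1% | 0.045/0.805 = 5.6% |

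In counts, treat all 150 planned PLAN-V participants (section 5) as otherwise eligible, with p = 10% and c1 = 0.40. There are 15 affected and 135 unaffected deliveries. Samples exist for 15 × 0.40 = 6 and 135 × 0.80 = 108. The report would show 6/114 = 5.3%, with 9 of the 15 events outside the analysis set.

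**Between cohorts.** Suppose both cohorts have a true 10% and c0 = 0.80, with c1 = 0.60 in one and 0.40 in the other. The observed frequencies are 7.7% and 5.3%. The false odds ratio is 0.40/0.60 = 0.67, or 1.5 in the other direction. If c1/c0 is the same in both cohorts, the odds ratio is undistorted, although each frequency is still biased unless c1 = c0.

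**Under the wider set.** If clinical outcomes are counted in all otherwise eligible mothers with a known outcome, c1 and c0 leave the formula and the expected frequency is p.

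**The case against.** The strongest reply is that Objective 3 is an immunology sub-study, designed as a cross-sectional analysis of delivery samples. Its clinical outcomes can be read as a description of the sampled dyads, with no test or safety conclusion attached. Safety belongs to Objective 2, whose outcomes in section 3.4.2 carry no sample requirement. This stands as a limit on scope: the main safety evaluation is untouched. It does not remove the point, because the sub-study's Data Sources paragraph looks to a comparison of health outcomes.

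A second reply is that the illustrated distortion is modest against sampling error. With 150 and 100 dyads and 10% risks, the standard error of a difference is √(0.09/150 + 0.09/100) = 3.9 percentage points. The assumed false contrast is 7.7 − 5.3 = 2.4 points. That is a fair measure of proportion, but bias does not shrink as numbers grow, and this one is avoidable.

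A reader might also infer three stronger claims that the document does not support:

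- **That stillbirths and emergency deliveries drop out.** The Protocol does not say that cord blood is missed in such births. Only off-site deliveries have support in the text, and that is indirect, since section 3.6.2 is silent on samples there.
- **That adverse frequencies are biased low.** This is plausible but cannot be derived. Equal collection gives no bias, and higher collection in complicated deliveries reverses it. For some outcomes in section 3.4.2, such as small size for gestational age, no reason for poorer collection is evident.
- **That Objective 3 contradicts section 3.5.7.** That section concerns exclusion from the study as a whole. A mother without cord blood stays in PLAN-V and in its other analyses, so a paired-sample subset is not a contradiction.

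**Conclusion.** The concern holds in a limited form. The Protocol itself ties Objective 3's clinical outcome frequencies to a post-exposure event that the outcomes can affect, and those outcomes do not need the samples. This is a stated eligibility rule rather than a detail left for a later analysis plan.

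The frequencies and the vaccination-versus-infection comparison of health outcomes may therefore be biased. Understatement of adverse outcomes is the more likely direction, but only if collection is less successful in complicated deliveries. The size is unknown: the range from 4.0% to 11.1% for a true 10% rests entirely on assumed collection rates. The comparison could be distorted either way, or hardly at all. Only the Objective 3 secondary outcomes are involved; its antibody endpoints properly keep the paired-sample set.

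**What to change.** Give the Objective 3 clinical outcomes their own population:

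- Keep the paired-sample dyads for the antibody endpoints.
- For pregnancy and newborn outcomes, use all otherwise eligible PLAN-V mothers (vaccinated in pregnancy, no history of COVID-19 infection) and all enrolled COPE mothers with a known pregnancy outcome in the COPE dataset, whether or not samples were collected. The infection-history criterion must stay, because section 3.2.2 admits previously infected women to PLAN-V and keeps those infected during the study; without it, infected mothers would enter the vaccinated group.
- Tabulate cord-collection success by outcome and by cohort, so that a reader can judge how selective the paired-sample set is.

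The change takes a sentence or two in Objective 3 and one table. For PLAN-V, chart extraction is already planned. For COPE, the Protocol does not show whether outcomes are held for mothers without samples, so this should be confirmed first. The costs are two denominators in one sub-study and some outcomes that remain missing, because retrieval after an off-site birth depends on a signed release.

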3.2.2. Exclusion criteria

Women/Individuals meeting any of the following criteria will not be eligible for participation in this study

- Cases with known major fetal concerns (e.g., major congenital malformations, chromosomal abnormalities) at the time of enrollment
- Women/Individuals who are fully vaccinated against COVID-19
- Women/Individuals who are pregnant due to surrogacy, or planning to give their child up for adoption
- Women/Individuals with a non-viable pregnancy (e.g., ectopic)

COVID-19 infection

- Women/Individuals previously infected with COVID-19 will be eligible for this study
- Women/Individuals who become infected with COVID-19 during the study period will be eligible to continue with the study protocol. COVID-19 infection (test-positive date, variant information) and symptomatology for both mother and infant (if applicable) will be documented.

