A baseline questionnaire will be administered **at enrollment** to document participant characteristics. We will collect socio-demographic information (e.g., maternal age, ethnicity, occupation, education, household income), medical and obstetrical histories (e.g., parity, pre-existing conditions), receipt of blood products or other vaccines in pregnancy, other lifestyle risks (e.g., tobacco, alcohol and other substance use), and previous SARS-CoV-2 infection history. Key factors influencing participant decision-making to receive the COVID-19 vaccine (decision needs, information access, family and societal pressures) will be documented.

Reactogenicity questionnaires

After each COVID-19 vaccine dose we will collect priority variables for studying COVID-19 vaccination in the maternal-newborn population¹¹:

- **COVID-19 vaccine data:** vaccine product (e.g., Moderna, Pfizer-BioNTech, Janssen (Johnson & Johnson), Oxford-AstraZeneca, etc.), dose number (one or two) and date received (to calculate timing of exposure in pregnancy or postpartum relative to delivery, and length of time between doses, if applicable). Scheduled dates of second COVID-19 vaccine doses (if applicable) will also be collected.
- **Reactogenicity:** injection site (e.g., bruising, swelling, pain) and systemic (e.g., fever, headache, muscle ache, fatigue) reactogenicity since the participant received the most recent vaccine dose.

General follow-up questionnaires

At each subsequent follow-up timepoint:

- **If the participant is still pregnant:** We will ask about significant changes in maternal and fetal health (e.g., new medical diagnoses or illnesses), maternal receipt of any blood products or other vaccinations, and any new maternal COVID-19 diagnoses (including variant information if known) since the last study visit.
- **If the participant is postpartum:** We will ask about significant changes in maternal and infant health (e.g., new medical diagnoses or illnesses), receipt of any blood products or other vaccinations (mother or infant), infant feeding method (e.g., mother's own breastmilk/chestmilk, donor milk, formula, other, combination) and infant growth (e.g., weight, length). We will also ask about any new maternal or infant COVID-19 diagnoses (including variant information if known) since the last study visit.

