3.7.3. Sample Analysis

Data derived from sample analysis will be linkable to the data file generated from primary and secondary data collection.

Antibody Response to Vaccination

[figure not shown]
Blood and breastmilk/chestmilk samples will be evaluated for antibodies to SARS CoV-2 and neutralizing antibodies to assess maternal and newborn immune responses to maternal vaccination in pregnancy. All samples will be analyzed using a high-throughput enzyme-linked immunosorbent assay based on previously published methods.^{12,13} The assay probes for IgA, IgM and IgG anti-SARS-CoV-2 antibodies and also maintains sensitivity in the detection of antibodies raised against variants of concern: P1, B.1.1.7 and B.1.351. The serological assay detects antibodies against the nucleoprotein (N), the receptor binding domain (RBD) and the full trimeric spike (S). Test sensitivity is 100% at 10 days post-symptoms and specificity is 99.2% as tested against pre-pandemic samples (manuscript in preparation). Such a strategy can distinguish infection-acquired immunity (against N+S+RBD) vs vaccine-induced immunity (S+RBD only). We will also run Neutralization assays (snELISA) on the full spike protein, based on previously published methods.¹⁴ A positive cut-off will be established, equal to the mean of the optical density (OD) values of the negative control samples on the respective plate plus 2x the standard deviation of the OD value distribution from pre-COVID-19 plasma/serum. Background-corrected OD values will be divided by the cut-off to generate signal-to-cutoff (S/CO) ratios. Samples with S/CO values greater than 1.0 will be considered positive. Relative antibody levels measured against a standard curve will also be reported.

Biomarker evaluation

To add understanding to the immunological microenvironment driving the quality and quantity of maternal and newborn antibody responses to maternal COVID-19 vaccination, serum samples will be analyzed for relevant biomarker expression (e.g., serum cytokines). Multiplex immunobead-based assays (BioRad) will be used to quantify serum cytokines.

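### The infection-naive sets for Objectives 3 and 4 rest on infection history and make no use of the anti-N result measured on the same samples, so unrecognised infections stay in the vaccine-only groups

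*Protocol*

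**What the plan says.** **Selection.** In the Objective 4 sub-study, the PLAN-V rule is "We will limit this analysis to women/individuals without known history of SARS-CoV-2 infection". The SSO comparator is "Non-pregnant females of reproductive age without known history of SARS-CoV-2 infection who received at least one COVID-19 vaccine dose". In the Objective 3 sub-study, the PLAN-V rule is "Eligible dyads will be those where mothers had no COVID-19 infection history"; here the qualifier about what is known is absent, and the term is not defined.

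**Where infection history comes from.** The baseline questionnaire in Section 3.6.1 collects "previous SARS-CoV-2 infection history", and follow-up questionnaires ask about new diagnoses. Section 3.2.2 adds, for infections during the study: "COVID-19 infection (test-positive date, variant information) and symptomatology for both mother and infant (if applicable) will be documented". Section 3.6.2 allows chart review to complete or verify the data.

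**What the laboratory measures.** Section 3.7.3 runs an assay for antibodies to nucleoprotein, receptor binding domain and spike on all samples, and says: "Such a strategy can distinguish infection-acquired immunity (against N+S+RBD) vs vaccine-induced immunity (S+RBD only". Both sub-studies refer to Section 3.7.3 for their sample analysis. Section 4 undertakes to account for COVID-19 infection history in all analyses.

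Nowhere does the protocol use the anti-N result to define, exclude or reclassify a participant.

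**The concern.** Both sub-studies restrict the vaccinated groups to women without infection so that the measured response reflects vaccination alone. Questionnaires, positive tests and charts can only exclude infections that somebody noticed. The protocol describes a laboratory marker for the rest, measures it on the same samples, and then selects without it. Under the rule as written, a woman who is anti-N positive but has no recorded infection counts as vaccine-only.

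The adjustment in Section 4 does not help. Recorded infections are already excluded from these sets, and unrecorded ones have no history to adjust for.

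Both comparisons are listed among the primary outcomes in Section 3.4.1. In Objective 3 the infection arm (COPE) is infected by design, so hidden infection affects only the vaccine arm. In Objective 4 it can affect both arms, and what matters for the contrast is whether it does so equally.

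**Working it through.** **Inputs from the protocol.** PLAN-V n = 150; stated power 93% to 95% for 95% versus 80% seroconversion at alpha 0.05; detectable geometric mean (GM) ratio 1.19 (all Section 5). COPE: more than 100 dyads, taken as 100. SSO: 126. Assay specificity 99.2% (Section 3.7.3).

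**Inputs assumed.** The share u of the vaccine-only set with unrecognised infection, and the fold-excess R in their titres. The protocol gives neither, so ranges are shown. Two-sided testing is also assumed.

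**Step 1: the plan's own power.** With the continuity-corrected normal approximation, power = Φ[(d − c − 1.96·se0)/se1], where d = 0.15, c = ½(1/n1 + 1/n2), se0 uses the pooled rate and se1 the separate rates.
- 150 v 100: pooled rate 0.890, se0 = 0.0404, se1 = 0.0438, c = 0.0083; power 92.3%.
- 150 v 126: pooled rate 0.882, se0 = 0.0391, se1 = 0.0398, c = 0.0073; power 95.2%.

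Without the correction the values are 94.7% and 96.7%. The stated 93% to 95% is reproduced to within 2 points and is not in dispute.

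**Step 2: effect on one arm's GM.** If the uninfected women have GM = G and a share u has R·G, then log GM = (1 − u)·log G + u·log(R·G) = log G + u·log R. The GM is multiplied by R^u.

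| u | R = 3 | R = 5 | R = 10 |
|---|---|---|---|
| 5% | 1.06 | 1.08 | 1.12 |
| 10% | 1.12 | 1.17 | 1.26 |

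For scale, R^u reaches 1.19 when u = ln 1.19 / ln R: about 16% for R = 3, 11% for R = 5 and 8% for R = 10.

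**Step 3: Objective 3.** Only the vaccine arm is affected, so the vaccine-to-infection GM ratio is multiplied by R^u, as in the table.

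**Step 4: Objective 4.** Both arms are vaccinated and selected alike, so the ratio of pregnant to non-pregnant GMs is multiplied by R^(u in PLAN-V − u in SSO), for R = 3 to 10:
- equal shares: 1.00;
- 10% v 5%: 1.06 to 1.12;
- 5% v 10%: 0.95 to 0.89.

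**Step 5: cost of using anti-N.** Assume that 99.2% applies to the N target and that errors are independent between samples.
- One test: 150 × 0.008 = 1.2 wrongly excluded.
- Two tests: 150 × (1 − 0.992²) = 2.4 in PLAN-V and 126 × (1 − 0.992²) = 2.0 in SSO.
- Every sample: 150 × (1 − 0.992⁶) = 7.1 for up to six maternal samples in Table 2, and 126 × (1 − 0.992¹⁰) = 9.7 for ten monthly SSO samples.

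If the mean + 2 SD cut-off in Section 3.7.3 governs N, the false-positive rate under normality is about 2.3%: 150 × 0.0228 = 3.4 for one test and about 6.7 for two.

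**Step 6: power after exclusion.** With two tests, true positives and false positives removed, COPE kept at 100, and the same continuity-corrected formula:

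| u in both cohorts | PLAN-V left | SSO left | Objective 3 | Objective 4 |
|---|---|---|---|---|
| 2% | 145 | 122 | 91.9% | 94.5% |
| 5% | 140 | 118 | 91.5% | 93.7% |
| 10% | 133 | 112 | 90.8% | 92.4% |
| 15% | 125 | 105 | 89.8% | 90.6% |

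**The case against.** **This belongs in an analysis plan.** How serology refines an infection-naive set is often settled there, and the protocol does not forbid using anti-N. But these populations are written into the protocol, and for Objective 4 the stated criterion is what is known. Someone following it keeps anti-N-positive women. The point concerns a rule that is stated, not a detail left out.

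**Objective 3 is worded differently.** This stands in part. Its rule does not say that the history must be known, and it could be judged with serology. Reading it as recorded history is an inference from Sections 3.2.2, 3.6.1 and 3.6.2. Even on the kinder reading, the term needs a definition, and the only one-directional bias depends on it.

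**Ascertainment is broader than self-report.** This also stands. Test-positive dates and chart review add to the questionnaires. They still miss infections that were never diagnosed.

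**Objective 4 uses one rule in both cohorts.** A reader might infer that the pregnant versus non-pregnant contrast is inflated. The documents do not support that: with equal hidden-infection shares the ratio does not move, and neither share is given. Nor do they show that the two cohorts were sampled over different periods. SSO is described as ongoing, and its follow-up as comparable across the PLAN-V time points. The difference the documents do show is geographic: SSO is Ottawa-based, while the COPE Network sites lie in six cities.

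**The size is assumed, and 1.19 is not a tolerance for bias.** Both are correct. The figure of 1.19 is a detectable ratio, used above only for scale.

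**Excluding on any anti-N positive has its own cost.** This is right and shapes the remedy. Requiring every sample to be negative would lose about 7 of 150 in PLAN-V and 10 of 126 in SSO to false positives, a loss that differs by arm because the cohorts are sampled unequally.

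**Conclusion.** The point holds, and a change should be made. Objective 4 selects on known infection history and Objective 3 on an undefined infection history, while a marker that the protocol itself presents as separating infection from vaccine response is measured and not used for selection.

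For Objective 3, if infection plus vaccination raises titres, the vaccine-to-infection ratio is biased upward by R^u. Over u = 5% to 10% and R = 3 to 10 that is 6% to 26%; both inputs are assumptions. For Objective 4, absolute titres are affected in both arms, but a bias in the contrast needs unequal hidden-infection shares. Its direction is unknown, and it may be zero. The stated power is sound and changes little under the remedy.

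**What to change.** In both sub-studies, define infection-naive as no recorded infection **and** anti-N negative at the analysed sample and at the baseline or first available sample. Apply this to PLAN-V in Objectives 3 and 4 and to SSO in Objective 4. Use the same number and timing of tested samples in PLAN-V and SSO, so that false-positive exclusions do not differ by arm. In longitudinal analyses, drop a participant's samples from a documented infection, or from a confirmed (repeated or sustained) anti-N positive, onward. State what counts as recorded infection, and report the history-only set as a sensitivity analysis.

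The cost is a few sentences, since the assay is already planned on these samples. About 2 of 150 would be wrongly excluded with two tests if 99.2% applies to N, and more if the mean + 2 SD cut-off governs it. The protocol should say which specificity applies to N. Some infections will still be missed: the quoted 100% sensitivity refers to 10 days after symptoms, so asymptomatic infections or those with waned anti-N may test negative.
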